The primary analysis of the designated endpoints will be calculated on an intention-to-treat basis. In cases where an arm was not completed (and that arm was not repeated according to protocol criteria) we will use the available data from that arm in the data analysis. We will only include arms that were started by the subject.

We will use the Shapiro-Wilk test to determine the normality of the residuals for each comparison and calculate percentages, means or medians, and standard deviation and/or ranges as appropriate in descriptive analyses. We will use paired t-test or the Wilcoxon signed rank test for comparison of means with normally or non-normally distributed residuals, respectively. In a secondary analysis we will look for any period effect and any interaction between treatment and period, although no such interaction is predicted for the primary outcome, and there is probably insufficient power to identify a small interaction.

VI. c. Power Analysis

The power analysis is based on data from previous studies using the iPhone-based BP. The following table shows the percentage of time that the insulin and glucagon pumps were available to deliver doses calculated by the bionic pancreas. When pumps were not available, this was typically due to loss of communication between the iPhone and the t:slim pumps, but could also be due to pump occlusion or inadequate drug in the reservoir, among many other possible reasons.

Table 1. Time that pumps were available in previous bionic pancreas studies

| Study | insulin | | Glucagon | |
|------------------------------|---------|-----|----------|-----|
| | Mean | SD | Mean | SD |
| Beacon Hill | 96.5 | 2.7 | 95.9 | 2.3 |
| Camp1 | 93 | 2.7 | 92.2 | 2.3 |
| Camp2 | 95.1 | 2.5 | 93.9 | 3.1 |
| Multi-center | 96.1 | 2.5 | 95.9 | 2.5 |
| Mean | 95.2 | 2.6 | 94.5 | 2.6 |
| Min | 93.0 | 2.5 | 92.2 | 2.3 |
| Max | 96.5 | 2.7 | 95.9 | 3.1 |
| ttest (insulin vs. glucagon) | | | 0.044 | |

The glucagon pump was unavailable a greater percentage of the time than the insulin pump in the iPhone-based BP. This could be due to more frequent reservoir changes (the glucagon reservoir had to be changed every day, while the insulin reservoir was changed every other day – the pumps were unavailable during the reservoir change process), greater number of occlusions in the glucagon tubing and infusion sets, or possibly other, unknown factors.

We anticipate that the iLet BP will be much more reliable in terms of delivering calculated doses because it does not rely on wireless communication between the device running the control algorithm and the pumps. In the iLet, the control algorithm and pumps are integrated into a single device. Nonetheless, there may still be times that the pump is unavailable or that the full dose is not delivered (e.g. due to temporary loss of communication between components due to software issue, tubing occlusion, or inadequate drug in the reservoir). Therefore, we anticipate that the percentage of the dose amount calculated that are delivered will be substantially greater, but not 100%.

We have modeled the power to detect a difference between the iPhone-based and iLet BPs based on an aggregate rate of pump unavailability of the iPhone-based BP (including both the insulin and glucagon pumps) of $96\pm 2.5\%$, which is close to the maximum reliability that we observed in the more reliable insulin pump across the 4 previous studies. We then calculated the power based on different possible reliabilities of the iLet internal pumping systems, based on 2-fold, 5-fold, and 10-fold reductions in pump unavailability, corresponding to availabilities of $98\pm 2.5\%$, $99.2\pm 2.5\%$, and $99.6\pm 2.5\%$, respectively. Under these assumptions, the sample sizes required for each of these possible outcomes to achieve a power of 80% with an alpha of 5% using a 2-sided test are 25 subjects, 10 subjects, and 8 subjects respectively. We expect a reduction of at least 5-fold in pump unavailability (and 10-fold would not be surprising), so 10 subjects should provide sufficient power to detect a difference. The standard deviations are assumed to be unchanged in these calculations, although it is likely that the standard deviations would also be reduced if the pump becomes more reliable - this means that the sample size estimates are likely conservative.

As the Infusion Set Sub-Study is a pilot study of the modified infusion set, no formal power calculations have been done for this portion of the study.

VI. d. Criteria for Success of the Study

The main criteria for the success of the study will be that we observe a significant improvement in the primary outcome measure (and the related secondary reliability measures) in the iLet vs. the iPhone-based BPs, and no significant difference in the glycemic control measures. It is possible that improved reliability may actually improve glycemic control measures, but the sample size may not be sufficient to detect any such difference. A secondary criterion for success of the study will be that we observe no statistical difference in safety-related outcomes (occlusions, infusion site reactions or pain, nausea) between Xeris and Lilly glucagon.

The main criteria for the success of the infusion set sub-study will be that we observe no significant difference in the performance of the iLet infusion set when compared with the Contact Detach. Achieving a non-inferior result would allow us to move forward in future testing of the iLet infusion set with the iLet bionic pancreas in outpatient trials.

VII. Risks and Discomforts

Subjects may experience mild discomfort associated with the insertion of the infusion sets and sensor into the SC tissues. The risk of discomfort due to insertion of infusion sets and sensors is expected to be greater than in their lives outside the trial because more infusion sets will be inserted and a CGM sensor will be inserted, which may not be used in usual care.

There is a potential risk of hypoglycemia, since exogenous insulin will be administered. Due to frequent monitoring of glucose and direct supervision by an RN or MD at all times, the risk of a hypoglycemic episodes leading to significant harm to volunteers is expected to be substantially lower than their risk during their usual therapy.

There is a risk of hyperglycemia. This risk is expected to be less than the risk during the subjects' lives outside of the trial based on data from earlier trials.

There is a risk of headache, nausea, or vomiting in subjects due to the administration of exogenous glucagon. This risk has been low in prior studies, and we expect it to remain so in this trial given its short duration. In our previous studies we found no significant difference between daily nausea scores (10 cm visual analog scale) on the bionic pancreas vs. usual care. We found the same in a study in which patients controlled their own insulin pump and got glucagon or placebo delivered by the bionic pancreas (randomized by day). In that study there was no difference in VAS nausea and subjects correctly guessed their treatment assignment on a given day only

42% of the time (less than chance). Therefore, the glucagon appears to be very well tolerated.

There is a risk of skin irritation at the site of the Xeris glucagon infusion. Based on previous studies using larger doses of Xeris glucagon, we expect any infusion site reactions to be mild and transient.

The risks of intravenous lines remaining in place for about 8 hours include thrombosis and phlebitis of the peripheral vein. Subjects may experience discomfort with insertion of the peripheral intravenous line.

There is a risk of risk of dizziness or lightheadedness from blood loss. However, typical blood loss will be less than 200 ml per visit. Furthermore, subjects will be disqualified from participation if they have a hemoglobin < 12 g/dl.

VII. a. Infusion Set Sub-Study risks:

Subjects may experience mild discomfort associated with the insertion of the infusion sets into the SC tissues. The risk of discomfort due to insertion of infusion sets is not expected to be greater than in their lives outside the trial.

There is a potential risk of hypoglycemia, since exogenous insulin will be administered. Due to frequent monitoring of glucose and direct supervision by an RN or MD at all times, the risk of a hypoglycemic episodes leading to significant harm to volunteers is expected to be substantially lower than their risk during their usual therapy.

There is a risk of hyperglycemia. This risk may be higher than their usual lives outside the trial due to the use of an investigational infusion set.

The risks of intravenous lines remaining in place for about 5 hours include thrombosis and phlebitis of the peripheral vein. Subjects may experience discomfort with insertion of the peripheral intravenous line.

There is a risk of risk of dizziness or lightheadedness from blood loss. However, typical blood loss will be less than 100 ml per visit. Furthermore, subjects will be disqualified from participation if they have a hemoglobin < 11g/dl.

VIII. Potential Benefits

Based on evidence from previous trials of the bionic pancreas and the design of this trial, subjects enrolled in the study may benefit from a reduction in risk of hypoglycemia and hyperglycemia and a better mean glucose compared to their usual diabetes care during their participation.

The data derived from this study will allow us to evaluate the robustness and effectiveness of the new bionic pancreas control system. The data obtained will be used to further improve the iLet BP and will allow us to expand to larger outpatient trials using the new device.

This study is a necessary step in preparing the bionic pancreas to become available to people with type 1 diabetes. Wide availability of the bionic pancreas could improve the care adults and children with type 1 diabetes.

Subjects will be financially compensated for participating in the study.

VIII. a. Infusion Set Sub-Study Potential Benefits

The data derived from this study will allow us to evaluate the robustness and effectiveness of the new iLet infusion set. The data obtained will be used to further improve the iLet BP and will allow us to expand to larger outpatient trials using the new device.

This study is a necessary step in preparing the bionic pancreas to become available to people with type 1 diabetes. Wide availability of the bionic pancreas could improve the care adults and children with type 1 diabetes.

Subjects will be financially compensated for participating in the study.

IX. Data and Safety Monitoring

IX. a. Monitoring of Source Data

During the experiment, CGM data, calibration data, insulin dosing data, and glucagon dosing data will be automatically stored in the bionic pancreas device (from which it will be downloaded at intervals). All of the data will be combined in a single database that will be compared against the primary data files for integrity. The computer database will be backed up at least monthly and the backup media stored in a secure location.

Study staff will be encouraged to raise any concerns they may have or problems they have identified at any time. The PI, in consultation with the co-investigators, will decide a course of corrective action, and resolution or progress will be assessed no later than the next meeting.

An audit of procedures, regulatory documentation, and a sample of subject files will be performed by a member of the Diabetes Research Center at least biannually. The audit will be conducted by a staff member who is not directly involved in the conduct of the study. This audit will include a review of regulatory documentation, such as IRB and FDA correspondence, and a review of subject files, including a review of consents, case report forms, and other data from study visits.

A numeric code will be substituted for the subjects personal identifying information in the study database, which will be password protected. The key linking the medical record number of the subject with the numeric code, along with case report forms, and all information that is personally identifiable, will be kept in a locked filing cabinet in an investigator's locked office. All electronic records will be kept in a password protected computer database. All printed computer data will be disposed of confidentially when no longer needed. Only the study staff will have access to the study database. Subjects may not withdraw from the de-identified database, but they may elect to have the key linking their medical record to the de-identified database destroyed.

The study data will be shared with collaborators at Beta Bionics, Inc. but only in a form in which all personally identifiable information has been removed (e.g. combined database including BG values, record of insulin and glucagon delivered by the device, and blood insulin and glucagon levels). Shared data will be in the form of a database in which only a number identifies subjects.

Subjects may not withdraw their data, as it will be stored in non-personally identifiable form.

IX. b. Safety Monitoring

This study is considered moderate risk. An external Data and Safety Monitoring Board will oversee the conduct of the study and review its results on a regular basis. Additionally, the DSMB will be informed in the event of any severe or unexpected adverse events. The DSMB will be informed if there are any changes to the study protocol that could significantly impact the safety or scientific validity of the study. A final DSMB meeting will convene after the completion of the study. Safety and efficacy data will also be reported to the FDA in compliance with applicable regulations.

As noted above, the participation of individual subjects will be discontinued if they experience:

- Seizure or unconsciousness associated with hypoglycemia
- Persistent nausea and vomiting thought to be related to glucagon dosing
- Persistent moderate or severe pain, edema or erythema at an infusion site
- Diabetic Ketoacidosis

If more than 1 subject must be withdrawn from the study for these reasons, the study will stop and a vote of the DSMB will be required to restart it. All serious and unexpected events will be reported to the DSMB within 72 hours.

Note that subjects may discontinue participation at any time and subjects may be removed from the trial for other reasons, for instance failure to comply with study procedures or intercurrent illness that is unrelated to the bionic

pancreas but that precludes safe participation. Discontinuation of participation for these reasons will not contribute to a decision to discontinue the trial.

IX. c. Adverse Event Reporting Guidelines

The PI and co-investigators will review any adverse events after each experiment. Any serious or unexpected but possibly related adverse events will be communicated to the PI as soon as possible and within 48 hours of the time they are detected. Adverse events will be reported promptly to the Partner's IRB. Collaborator [name] is the sponsor of the Investigational Device Exception (IDE) for the bionic pancreas to be used in this trial. Reports of adverse events will be made to the FDA in compliance with the terms of IDE.

X. Subject Compensation

Financial compensation will be provided to all subjects who complete the screening visit. Subjects will be paid \$25 for completing the screening visit whether or not they are eligible to participate in the study. Study participants will be compensated \$150 for completing the three study visits. Thus the total compensation for a subject who completed the study would be \$175. Parking expenses will be paid for up to \$30 per subject, and lunches will be paid for up to \$100 per subject (50 dollars per lunch). Subjects who are unable to complete the study or chose to stop participation will receive prorated compensation at a rate of \$50 per completed day. In addition to the monetary compensation, the cost of the subjects lunch meals during their participation in the study will be covered by study funds.

X. a. Infusion Set Sub-Study Compensation:

Financial compensation will be provided to all subjects who complete the screening visit. Subjects will be paid \$25 for completing the screening visit whether or not they are eligible to participate in the study. Study participants will be compensated \$50 for completing each study visit. Thus the total compensation for a subject who completed the study would be \$125. Parking expenses will be paid for up to \$30 per subject, and breakfast will be paid for up to \$40 per subject (20 dollars per meal).

XI. References

1. The Diabetes Control and Complications Trial research Group (DCCT) (1993) The effect of intensive treatment of diabetes on the development and progression of long-term complications in insulin dependent diabetes mellitus. *N. Engl. J. Med.* 329, 977–986.
2. The Diabetes Control and Complications Trial/Epidemiology of Diabetes Interventions and Complications (DCCT/EDIC) Study Research Group (2005) Intensive Diabetes Treatment and Cardiovascular Disease in Patients with Type 1 Diabetes. *N. Engl. J. Med.* 353, 2643–2653.
3. El-Khatib, F. H., Jiang, J., Gerrity, R. G. & Damiano, E. R. (2007) Pharmacodynamics and stability of subcutaneously infused glucagon in a type 1 diabetic swine model in vivo. *Diabetes Technol. & Ther.* 9, 135-144
4. El-Khatib, F. H., Jiang, J. & Damiano, E. R. (2007) Adaptive closed-loop control provides blood-glucose regulation in vivo using dual subcutaneous of insulin and glucagon infusion *Diabetes Sci. & Technol.* 2, 181-192.

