The preclinical studies at BU testing the BP in a diabetic swine model of T1D (3-4), and all of the inpatient clinical trials in the Clinical Research Center at MGH testing the BP in adults and adolescents with T1D (5-7) set the stage for the outpatient studies that followed. In November 2012 we obtained FDA approval to conduct our first outpatient study testing our BP in adults 21 years or older with T1D. This study, which we referred to as the Beacon Hill Study, followed a random-order cross-over design in which 20 adults with T1D participated in 5 days on our iPhone-based BP and 5 days of usual care in which they wore a CGM with blinded display and muted alarms. In the BP arm, subjects kept to a three-square-mile geographic area centered around the Beacon Hill neighborhood in Boston. They ate as they chose at local restaurants, and exercised at will with access to two gyms. Analysis was pre-specified to focus on Days 2--5, since glycemic control is more representative of BP performance after most of the adaptation by the BP occurs on Day 1 (8). Results are summarized in the plots and table of Figure 1.

| Study | Age (years) | Bionic Pancreas (BP) | | | Control | | | p-value (BP versus Control) for: | | |
|--|-------------|--------------------------------|--|------------------|--------------------------------|--|------------------|----------------------------------|------------------------------------|--------------------------------------|
| | | Mean CGM glucose level (mg/dl) | % of CGM glucose levels < 60 mg/dl (%) | 70–180 mg/dl (%) | Mean CGM glucose level (mg/dl) | % of CGM glucose values < 60 mg/dl (%) | 70–180 mg/dl (%) | Mean CGM glucose level | % of CGM glucose values < 60 mg/dl | % of CGM glucose values 70–180 mg/dl |
| Beacon Hill (n=20, 5-day experiments) | ≥21 | 133 | 1.5 | 80 | 159 | 3.7 | 59 | <0.001 | 0.020 | <0.001 |
| 2013 Summer Camp (n=32, 5-day experiments) | 12–20 | 142 | 1.3 | 76 | 158 | 2.2 | 65 | 0.004 | 0.192 | <0.001 |
| 2014 Summer Camp (n=19, 5-day experiments) | 6–11 | 137 | 1.2 | 81 | 168 | 2.8 | 58 | 0.004 | 0.001 | <0.001 |
| BP Multi-Center (n=39, 11-day experiments) | ≥18 | 141 | 0.6 | 78 | 162 | 1.9 | 62 | <0.001 | <0.001 | <0.001 |

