We hypothesize that the iLet BP will be non-inferior to the iPhone-based BP in dose administration and blood glucose control while subsequently improving user satisfaction with the device. We also hypothesize that Xeris glucagon in the iLet BP will be non-inferior to Lilly glucagon in the iLet BP in both infusion site reactions and occlusions.

In the Infusion Set Sub-Study, we hypothesize that the iLet infusion set will be non-inferior to the Contact Detach infusion set in plasma insulin levels, blood glucose control, and user experience.

The specific aims of this study are:

Aim 1. To conduct an outpatient study testing the safety and efficacy of the iLet BP versus our iPhone-based BP in up to 10 adult (≥ 18 years of age) subjects with type 1 diabetes in the fasted state, after a meal, and during and after exercise.

The study for this Aim will consist of two 8-hour study arms in random order: one with the iPhone-based BP and one with the iLet BP. Subjects will arrive fasting and remain fasted until the lunch meal. They will exercise on a stationary bike bpm for approximately 30 minutes with a heart rate from 120–140, starting at least 2 hours after lunch. The primary outcome will be the average percent dose amounts of both insulin and glucagon calculated by the control algorithm that are successfully delivered by the pump. Important secondary outcomes will include other metrics of device function (plasma insulin and glucagon levels will be measured every 30 minutes throughout the experiment) and measures of glycemic regulation, including mean CGM glucose and hypoglycemia exposure (% time <60 mg/dl).

Aim 2. To conduct an outpatient study testing the safety and efficacy of the iLet BP with Lilly glucagon versus Xeris glucagon in up to 10 adult (≥ 18 years of age) subjects with type 1 diabetes

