- Date of last menstrual period in female subjects
- Date of diabetes diagnosis
- Medical, surgical, and social history, allergies, and review of systems relevant to inclusion and exclusion criteria
- Medications (prescription and non-prescription) and date of last change in medication regimen
- Duration of insulin pump use

- Type of insulin used in pump
- Insulin regimen (basal rate, sensitivity factor, and carbohydrate ratio)
- Average total daily dose of insulin in the last 30 days as available (from pump history)
- Usage of CGM, if any (type of CGM, days per month worn, usage of data, whether insulin is dosed based on CGM alone, alarm settings)
- Height and weight
- Blood pressure
- Hemoglobin A1c
- Urine HCG (pre-menopausal females)
- Fractionated plasma metanephrines (if indicated by history)

VI. a. 2. During study visits:

- CGMG (CGM glucose) every five minutes from the DexCom G4 Platinum CGM
- All BG measurements taken
- Insulin total daily dose
- Glucagon total daily dose
- Timing and content of the meal eaten and carbohydrate amount
- Timing of meal announcement and size of meal announced
- Timing and glucose values at calibrations
- Timing and amount of carbohydrates taken for hypoglycemia
- Time subjects were not under bionic pancreas control for any reason
- List of technical faults associated with the bionic pancreas including cause and resolution
- Nausea on a visual analog scale at study start, every 2 hours, and at study end
- Infusion site pain at study start (after insertion and before any drug administration), every 2 hours, and at study end
- Infusion site reaction according to the Draize scale at study start (after insertion and before any drug administration), every 2 hours, and at study end
- Infusion site appearance every 15 minutes (presence/absence of moisture, evidence site has been displaced)
- Timing of any infusion site replacements
- Subject reports of symptoms of any other complaints
- Timing of exercise and duration
- Volunteer reported Borg scale score for exercise intensity every 5 minutes during exercise
- Heart rate during exercise from Polar heart rate monitor every 5 minutes
- Plasma insulin levels every 30 minutes throughout the experiment
- Plasma glucagon levels every 30 minutes throughout the experiment

VI. a. 3. During the Infusion set Sub-Study:

At Screening:

- Age
- Sex
- Race and ethnicity
- Date of last menstrual period in female volunteers
- Date of diabetes diagnosis

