 - Fraction of time spent within each of the following glucose ranges:
 - < 50 mg/dl.
 - < 60 mg/dl.
 - < 70 mg/dl.
 - 70-120 mg/dl.
 - 70-180 mg/dl.
 - >180 mg/dl.
 - >250 mg/dl.
 - Percentage of subjects with mean CGM glucose < 154 mg/dl (estimated average glucose corresponding to an A1c of 7%).
- Number of severe hypoglycemic events (subject unable to self-treat, requiring the assistance of another person).

During Exercise

- Number of subjects discordant for reaching a BG < 60 mg/dl (measured with YSI) for > 2 consecutive plasma glucose measurements
- Area between the glucose curve and 60 mg/dl calculated from BG measurements
- Area between the glucose curve and 60 mg/dl calculated from CGM data
- Time from start of exercise to first BG measurement < 60 mg/dl
- Time from start of exercise to first CGM measurement < 60 mg/dl

VI. b. 5. Secondary endpoint analyses – Non-glycemic

- Glucagon total delivery per kg of body mass.
- Insulin total delivery per kg of body mass.
- Number of episodes of symptomatic hypoglycemia.
- Number of carbohydrate interventions for hypoglycemia.
- Total grams of carbohydrate taken for hypoglycemia.

- Difference in mean nausea from VAS during the study (mean of measurements every 2 hour and at study end) vs. baseline at study start.
- Difference in Infusion site pain from VAS during the study (mean of measurements every 2 hour and at study end) vs. baseline at study start. Note that in the iLet infusion set the infusion catheters are 1 cm apart, so it may not be possible to differentiate whether a sensation is coming from the insulin or glucagon infusion catheter. Subjects will be asked to use their best judgment and to provide scores for both catheters.
- Difference in local erythema and edema according to the Draize scale (mean of measurements every 2 hour and at study end) vs. baseline at study start. Note that in the iLet infusion set the infusion catheters are 1 cm apart, so it may not be possible to differentiate whether a skin reaction is coming from the insulin or glucagon infusion catheter. Subjects will be asked to use their best judgment and to provide scores for both catheters.
- Number of unscheduled infusion set replacements.
- Number of unscheduled CGM sensor changes.

During Exercise

- Grams of oral carbohydrates given to the subject to treat hypoglycemia
- Total glucagon dosing by bi-hormonal bionic pancreas from the start of exercise until the end of the visit

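### With 10 subjects and 8-hour visits, non-significance on time below 60 mg/dl does not show similar hypoglycemia control, yet VI.d counts it toward success

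*Combined protocol and SAP*

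**What the plan says.** Section II (Aim 1): "The study for this Aim will consist of two 8-hour study arms in random order". Aims 1 and 2 both list among their important secondary outcomes "measures of glycemic regulation, including mean CGM glucose and hypoglycemia exposure (% time <60 mg/dl". Up to 10 subjects are expected to complete (IV.a).

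VI.b.4 lists the glycemic endpoints. For hypoglycemia these are time below 50, 60 and 70 mg/dl, severe events, and exercise measures tied to 60 mg/dl, such as "Area between the glucose curve and 60 mg/dl calculated from BG measurements" (which I read as the area below 60). VI.b.5 separately lists symptomatic episodes, carbohydrate interventions and grams, and glucagon dosing from the start of exercise.

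The analysis paragraph after VI.b.5 says "We will use paired t-test or the Wilcoxon signed rank test for comparison of means", with the choice made by a Shapiro-Wilk test. VI.d requires, for iLet versus iPhone, a significant improvement in dose delivery and "no significant difference in the glycemic control measures". Section II hypothesizes non-inferiority in glucose control. Section I.d gives the purpose as establishing equivalence of the two systems, chiefly in function, user safety, accuracy and reliability. No margin is stated.

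**The concern.** A rule that is met by failing to find a difference rewards low information. It is weakest for a rare outcome, measured over a few hours, in about 10 people. Time below 60 mg/dl also ignores how low glucose went in anyone who stayed at or above 60, so many subjects may score zero at both visits.

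This is the first human use of the iLet. Aim 1 results are reviewed before Aim 2 starts, and the study is meant to support larger trials. If the iLet let glucose run lower after exercise, this part of the success criterion could still be met.

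**Working it through.** 1. **The plan's own power figure.** VI.c covers dose delivery only. With n = 2(1.96 + 0.842)² × SD² / Δ², SD 2.5 and Δ = 2, 3.2 and 3.6 points, n = 24.5, 9.6 and 7.6, rounding up to the stated 25, 10 and 8. No such calculation exists for any hypoglycemia measure.

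2. **Expected exposure.** The table in I.c gives, for adults, "BP Multi-Center (n=39, 11-day experiments) | ≥18 | 141 | 0.6 | 78 | 162 | 1.9 | 62" and "Beacon Hill (n=20, 5-day experiments) | ≥21 | 133 | 1.5 | 80 | 159 | 3.7 | 59". So 0.6% and 1.5% of readings were below 60 on the bionic pancreas, and 1.9% and 3.7% under usual care. CGM is recorded as "CGMG (CGM glucose) every five minutes from the DexCom G4 Platinum CGM", so 8 hours is 480 minutes or 96 readings.
   - 480 × 0.006 = 2.9 minutes (0.58 readings)
   - 480 × 0.015 = 7.2 minutes (1.44 readings)

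3. **Ties at zero.** The documents give no episode length, so I assume a range of lengths L, with episodes occurring at random (Poisson) and equal arms. P(zero at both visits) = exp(−2 × 480 × rate / L). The signed-rank test in its standard form drops zero differences. Its smallest two-sided p is 2/2⁵ = 0.0625 with 5 non-zero pairs and 2/2⁶ = 0.031 with 6, so at least 6 are needed.

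| Rate | L (min) | Pairs tied at zero | P(at least 6 of 10 pairs not both zero) |
|---|---|---|---|
| 0.6% | 10 | 56% | 24% |
| 0.6% | 20 | 75% | 2% |
| 0.6% | 30 | 83% | 0.3% |
| 1.5% | 10 | 24% | 94% |
| 1.5% | 20 | 49% | 41% |
| 1.5% | 30 | 62% | 14% |

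4. **Power of the planned rule.** I simulated Shapiro-Wilk followed by the paired t or exact signed-rank test, with n = 10, mean L of 10 to 30 minutes, with and without between-subject variation (gamma, CV 1), and 1,500 runs per setting.

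| True change in % time <60 | Power |
|---|---|
| 0.6 to 1.2 (doubling) | 0.1–7% |
| 1.5 to 3.0 (doubling) | 2–21% |
| 0.6 to 1.9 (usual-care rate) | 0.5–25% |
| 1.5 to 3.7 (usual-care rate) | 5–36% |
| 0.6 to 3.0 (fivefold) | 5–57% |
| 1.5 to 7.5 (fivefold) | 31–93% |

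5. **Rough cross-check.** Assume the I.c p-values come from paired t-tests. For the 20-subject study the difference is 2.2 points and p = 0.020 gives t = 2.54, so SD = 2.2 × √20 / 2.54 = 3.9 points. For the 39-subject study the difference is 1.3 points and p < 0.001 gives t of at least 3.57, so SD is at most 1.3 × √39 / 3.57 = 2.3 points. At n = 10 a paired t-test then has 80% power for about 3.9 and 2.3 points respectively, well above the 0.6% to 1.5% rates. These SDs come from multi-day comparisons with usual care, so they are only a guide.

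6. **Would a full-scale measure help?** I simulated 10 pairs with autocorrelated log-glucose (90-minute time constant, between-visit correlation 0.3). One arm was 10, 15 or 20 mg/dl lower throughout and a further 20, 30 or 40 lower at the exercise trough. Signed-rank power on % time <60, against paired t power on the YSI nadir:
   - 0.3% base exposure: 0/2/8% against 18/39/63%
   - 0.9% base exposure: 3/10/25% against 19/33/55%
   - 2.4% base exposure: 8/23/40% against 17/35/56%

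**The case against.** A reader might infer more than the documents support, in three ways.

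- **That hypoglycemia is compared only through glucose cuts.** It is not. Severe events are in VI.b.4, and VI.b.5 has symptomatic episodes, carbohydrate treatment and exercise-period glucagon dosing. The last is continuous and, by I.b, can respond before glucose is low. The event and carbohydrate counts are likely to be sparse, and carbohydrate treatment is partly triggered at 60 and 50 mg/dl. All but severe events are listed as non-glycemic, so VI.d's glycemic condition does not clearly reach them.
- **That the earlier rates predict mostly tied pairs and near-automatic non-significance.** The rates are multi-day free-living averages, one of them from Days 2–5 after adaptation. These visits start from weight alone and include fasting and exercise, so exposure could go either way. At 1.5%, most pairs tie only if episodes last about 21 minutes or more, and a fivefold rise from 1.5% would often be detected.
- **That nadir should replace percent time below 60.** The gain in step 6 rests on an assumed downward shift of the whole curve, which favors full-scale measures and would also move mean CGM glucose. Nadir still has only 17–19% power for the smallest shift and 33–39% for the middle one. The 60 mg/dl cut was co-primary in all four earlier studies, so keeping it preserves comparability.

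It is also fair that these are secondary outcomes in a small study that leaves comprehensive efficacy to larger trials. VI.d concedes that the sample may be too small to detect a glycemic difference, but only for an improvement. None of this makes non-significance evidence of similar control.

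**Conclusion.** The concern holds for the success rule. VI.d accepts non-significance where section II claims non-inferiority. For percent time below 60, that result is likely with 10 subjects even if exposure doubles (power about 0.1–21%) or rises to the usual-care rate (0.5–36%). These figures assume exposure near 0.6–1.5% and random episodes of 10 to 30 minutes, neither of which the documents establish for these visits. The missing margin or interval does not depend on those assumptions. The choice of 60 mg/dl is not itself an error.

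**What to change.** - **VI.d:** do not count non-significance of the time-below-threshold and area-below-60 measures as evidence of success. Report the paired difference in each hypoglycemia measure with a 95% confidence interval, and base the conclusion on what the interval excludes.
- **VI.b.4:** keep percent time below 60 for comparability. Add one prespecified full-scale low-glucose measure from the YSI data: a low blood glucose index, or the nadir over the visit and from exercise start to visit end.
- **Sampling:** compute the new measure on a common fixed grid, for example the scheduled draws only (every 15 minutes, every 10 during exercise). Otherwise the extra draws triggered below 80 mg/dl could drive it. State how values after rescue carbohydrate are handled.

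The cost is wording and a little analysis, with no new samples or visits. Nadir is a single extreme value and less familiar than time below range. Its advantage depends on assumptions, is largest at low exposure, and leaves small shifts underpowered, so the interval is the main benefit.
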